5.2. Medical History

Clinically relevant medical history (ie, conditions not specific to the disease being studied that are clinically relevant) will be listed only. General medical history will not be coded.

6. EFFICACY ANALYSES

6.1. Primary Efficacy Endpoint

6.1.1. Definition of the Primary Efficacy Endpoint

The primary efficacy endpoint is SVR12, defined as HCV RNA < LLOQ (ie, 15 IU/mL) 12 weeks after cessation of treatment in the FAS. The COBAS® AmpliPrep/COBAS® TaqMan® HCV Quantitative Test, version 2.0 will be used to measure and report HCV RNA results.

6.1.2. Statistical Hypothesis for the Primary Efficacy Endpoint

No hypothesis testing will be performed.

6.1.3. Analysis of the Primary Efficacy Endpoint

The estimate of SVR12 and a 2-sided 95% CI calculated using the Clopper-Pearson method {Clopper et al 1934} will be provided for the “SOF/VEL 4 Week” treatment group.

6.1.4. Subgroup Analysis of the Primary Efficacy Endpoint

Point estimates and the 2-sided exact 95% CI calculated using the Clopper-Pearson method will be presented for each subgroup presented in Section 3.4.

6.2. Secondary Efficacy Endpoints

6.2.1. Definition of Secondary Efficacy Endpoints

Secondary efficacy endpoints to be summarized for the “SOF/VEL 4 Week” treatment group for subjects in the FAS include:

- The proportion of subjects with SVR at 4 weeks after cessation of treatment (SVR4)
- The proportion of subjects with HCV RNA < LLOQ by visit while on treatment
- The proportion of subjects with VF. End of treatment VF and relapse will be defined by:

End of Treatment Virologic Failure: HCV RNA \geq 15 IU/mL at last observed HCV RNA measurement on or prior to last dose date of SOF/VEL + 3 days after completion of 28 ± 3 days of SOF/VEL treatment.

Relapse: HCV RNA \geq 15 IU/mL during the posttreatment follow-up period having achieved HCV RNA < 15 IU/mL at the end of treatment, confirmed with 2 consecutive values or last available posttreatment measurement.

6.2.2. Analysis Methods for Secondary Efficacy Endpoints

All secondary efficacy endpoints will be evaluated for the “SOF/VEL 4 Week” treatment group for subjects included in the FAS. For analyses of HCV RNA < LLOQ by visit while on treatment and during the posttreatment (SVR) follow-up period, subjects will be assigned a value at each visit based on the analysis visit windows specified in Section 3.8.2. Missing values will be imputed based on the categorical imputation rules described in Section 3.6.1. Estimates of the proportion of subjects < LLOQ by visit and the 95% exact CI using the Clopper-Pearson method will be calculated. The overall category for “HCV RNA < LLOQ” will be split into the subcategories “< LLOQ TND” for subjects with target not detected and “< LLOQ detected” for subjects with < LLOQ in tabular displays.

A summary table of the number and proportion of subjects with SVR12, VF, and Other will be presented for the “SOF/VEL 4 Week” treatment group. All subjects who achieve SVR12 will be categorized as SVR12. VF will be summarized for “end of treatment failure” and “relapse” (relapse will be broken down by study drug completed yes/no). Subjects who do not achieve SVR12 or VF will be categorized as Other.

The denominator for relapse will be the number of subjects who had HCV RNA < LLOQ on their last observed on-treatment HCV RNA measurement; the denominator for end of treatment response will be the number of subjects who completed 28 ± 3 days of treatment; otherwise, the denominator will be the number of subjects in the FAS.

For analyses of HCV RNA < LLOQ by visit while on treatment, subjects will be assigned a value at each visit based on the categorical imputation rules described in Section 3.7 of this SAP. Subjects with HCV RNA < LLOQ will be displayed into 2 subcategories: < LLOQ TND and < LLOQ detected. Point estimates and 2-sided exact 95% CIs using the Clopper-Pearson method will be displayed for the proportion of subjects < LLOQ at each visit.

A listing of HCV RNA (\log_{10} IU/mL) will be provided for FAS subjects, FAS subjects with VF, and FAS subjects with Other Virologic Outcome.

Drug resistant substitutions will be discussed as part of the clinical study report.

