### 8.3. Data Handling Conventions

Missing data can have an impact upon the interpretation of the trial data. Other than the endpoints discussed below, values for missing data will not be imputed.

For the analysis of post-Day 1 categorical efficacy endpoints, if a data point is missing and is preceded and followed in time by values that are deemed successes, then the missing data point will be termed a success; otherwise the data point will be termed a failure.

If no HCV RNA values are obtained after the last dose of study medication, the subject will be considered a treatment failure for the SVR endpoints. Subjects who have HCV RNA  $\geq$  LLOQ at end of treatment or relapse in off-treatment follow-up will be counted as failures at subsequent follow-up visits (ie, where no data is available).

Where appropriate, safety data for subjects that did not complete the study will be included in summary statistics. For example,

- If a subject received study medication, the subject will be included in a summary of adverse events according to the treatment received; otherwise, if the subject is not dosed then they will be excluded from the summary.
- If safety laboratory results for a subject are missing for any reason at a time point, the subject will be excluded from the calculation of summary statistics for that time point. If the subject is missing a pre-dose value, then the subject will be excluded from the calculation of summary statistics for the pre-dose value and the change from pre-dose values.

Values for missing safety laboratory data will not be imputed; however, a missing Day 1 result will be replaced with the most recent non-missing screening result, if available.

Values for missing vital signs data will not be imputed; however, a missing Day 1 result will be replaced with the most recent non-missing screening result, if available.

HCV RNA values below the LLOQ for the assay will be set to the lower limit minus 1 for calculation of summary statistics for the actual HCV RNA value. The reported values will be provided in the HCV RNA listing.

For selected analyses of early time point data, HCV RNA data (IU/mL) may be transformed to the logarithmic (base 10) scale ( $\log_{10}$  IU/mL).

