1.3. Sample Size

A total of 10 subjects are expected to be enrolled, receive a transplant, and be dosed with SOF/VEL. With a sample size of 10 subjects, a 2-sided 95% exact confidence interval (CI) will extend at most 63% in length.

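### The relapse denominator in SAP 6.2.2 includes end-of-treatment responders with no post-treatment HCV RNA, who can never be counted as relapses

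*SAP*

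**What the plan says.** Three rules bear on a subject who is below LLOQ at the last on-treatment sample and then provides no post-treatment sample.

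- **Denominator (SAP 6.2.2).** "The denominator for relapse will be the number of subjects who had HCV RNA < LLOQ on their last observed on-treatment HCV RNA measurement". No post-treatment value is required.
- **Numerator (SAP 6.2.1).** Relapse is a post-treatment HCV RNA of at least 15 IU/mL in a subject who was below that level at end of treatment, "confirmed with 2 consecutive values or last available posttreatment measurement". Either form of confirmation needs an observed post-treatment result.
- **SVR (Protocol 8.3).** "If no HCV RNA values are obtained after the last dose of study medication, the subject will be considered a treatment failure". This rule is limited to SVR and does not mention relapse. SAP 3.6.1 agrees, because it scores an unbracketed missing value as a failure.

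SAP 6.2.2 also defines the outcome table. "Subjects who do not achieve SVR12 or VF will be categorized as Other", and apart from relapse and end-of-treatment response, "otherwise, the denominator will be the number of subjects in the FAS". The analysis is descriptive: "No hypothesis testing will be performed".

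**The concern.** A rate is easiest to read when everyone in the denominator could have been seen to have the event. Here a responder without follow-up sits in the denominator of a rate whose numerator that subject cannot enter. The subject is a failure for SVR but has the arithmetic effect of a non-relapser in the relapse row.

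The situation is plausible. First dosing falls on the day of liver transplantation or shortly after (Protocol 3.3), and deaths and graft losses are named safety endpoints (Protocol 8.1.4). SAP 4.1.3 already plans a count of subjects with no Week 4 post-treatment HCV RNA. Because the denominator uses the last observed on-treatment value, it also keeps a subject who dies during treatment while suppressed.

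There is a second, smaller gap. SAP 3.6.1 imputes missing post-treatment categorical HCV RNA as failure, and SAP 6.2.2 applies that to the by-visit analyses. No sentence says whether it also feeds the relapse derivation. The existence of the Other category implies that it does not, but a programmer has to infer this.

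At stake is how one sub-row of the virologic outcome table is read.

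**Working it through.** **The plan's own figure.** SAP 1.3: "With a sample size of 10 subjects, a 2-sided 95% exact confidence interval (CI) will extend at most 63% in length". SAP 6.1.3 specifies a "2-sided 95% CI calculated using the Clopper-Pearson method" for SVR12. For n = 10 the widest such interval is at x = 5, from 18.7% to 81.3%. Its length is 62.6%, so the stated 63% is reproduced.

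**Inputs for the relapse rate.**
- D = responders, that is, subjects below LLOQ at the last on-treatment value. Assumed to be 10, the planned sample size and so the largest planned value.
- m = responders with no post-treatment HCV RNA. Not given in the documents; 0, 1 and 2 are shown.
- r = observed relapses. Not given for this regimen; 0 to 3 are shown.

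**Formulas.**
- Planned rate (SAP 6.2.2) = r / D
- Rate among evaluable responders = r / (D - m)
- Hence planned rate = evaluable rate × (1 - m/D). For example, 1/9 × 9/10 = 1/10.

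**Results for D = 10.** Clopper-Pearson 95% intervals are in brackets. They are added here for scale, since the plan does not specify an interval for relapse.

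| r | Planned, r/10 (same as m = 0) | m = 1, r/9 | m = 2, r/8 |
|---|---|---|---|
| 0 | 0.0% (0.0 to 30.8) | 0.0% (0.0 to 33.6) | 0.0% (0.0 to 36.9) |
| 1 | 10.0% (0.3 to 44.5) | 11.1% (0.3 to 48.2) | 12.5% (0.3 to 52.7) |
| 2 | 20.0% (2.5 to 55.6) | 22.2% (2.8 to 60.0) | 25.0% (3.2 to 65.1) |
| 3 | 30.0% (6.7 to 65.2) | 33.3% (7.5 to 70.1) | 37.5% (8.5 to 75.5) |

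For one to three relapses the gap is 1.1 to 3.3 percentage points with m = 1 and 2.5 to 7.5 points with m = 2. In relative terms the planned rate is 10% or 20% below the evaluable rate. With m = 0 nothing moves. With r = 0 only the upper confidence limit moves.

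**If the SAP 3.6.1 imputation were applied to relapse.** The missing subjects would then count as relapses and the rate would be (r + m)/D. With D = 10, m = 1 and r = 1 this is 2/10 = 20%. The same data would give 10.0%, 11.1% or 20.0% depending on the reading.

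**The case against.** The strongest reply is that nothing is hidden and no endpoint moves. A responder without follow-up is not presented as a success. The subject is an SVR12 failure, appears under Other in the same table, and is listed individually in Listing 22.2. Listing 21 gives HCV RNA by visit for the whole FAS, so with about 10 subjects a reader can recompute the alternative rate. The secondary endpoint is the proportion with virologic failure, which uses the FAS denominator. All of this stands, and it limits the point to one descriptive rate.

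It is also fair to say that m is likely to be small. A subject who completes treatment must miss all four post-treatment visits to have no value, and Protocol 3.5 and 6.7 call for follow-up after early discontinuation. Observed relapses among all responders is, moreover, a coherent quantity if it is labelled as such.

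Three stronger readings may tempt a reader, and the documents do not support them.

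- *Everyone who dies or leaves after responding counts as a non-relapser.* A subject whose last available post-treatment value is 15 IU/mL or more is a relapse under SAP 6.2.1. A subject who leaves after a post-treatment value below LLOQ stays in the denominator under either definition.
- *The relapse rate is biased low as a matter of fact.* That requires at least one responder without follow-up and some relapse risk in such subjects. The documents give a figure for neither.
- *The relapse and SVR tables contradict each other.* They do not, because the Other category accounts for the subject.

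The objection leaves one thing unanswered: the numerator and denominator of the relapse rate do not cover the same subjects, and the wording is silent on imputation.

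**Conclusion.** The point holds as a minor improvement. As written, the relapse rate is the evaluable-subject rate multiplied by (1 - m/D), so it is equal or lower, never higher, provided that imputation is not applied to relapse. With 10 responders, one relapse and one or two of them without follow-up, 10.0% is reported where 11.1% or 12.5% of evaluable responders relapsed. That shift is small beside the exact interval for 1/10 (0.3% to 44.5%). The size rests on assumed values of D, m and r; only the direction follows from the wording. The primary endpoint, SVR4 and the FAS-based virologic failure proportion are untouched, and no test or decision rule depends on this rate.

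**What to change.** In SAP 6.2.2:

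1. Define the relapse denominator as subjects with HCV RNA < LLOQ at the last on-treatment measurement and at least one post-treatment HCV RNA measurement. Alternatively, keep the current rate and report this one beside it.
2. State that the missing-equals-failure imputation in SAP 3.6.1 is not used to derive relapse.
3. In Table 10, under Other, show the number of responders with no post-treatment HCV RNA value.

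The cost is one or two sentences and one table row, using data already collected. If the SAP is already final, its Introduction provides for recording the change in the CSR. The downside is a denominator that may be one or two smaller and a slightly less favourable rate. The change does not deal with subjects who leave after an early post-treatment value below LLOQ. They remain in the denominator, and a footnote should say so.

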6.3. Exploratory Efficacy Analysis

None

6.4. Changes From Protocol-Specified Efficacy Analyses

None

7. SAFETY ANALYSES

Safety data will be summarized for the SOF/VEL 4 Week group for the Safety Analysis Set.

7.1. Adverse Events and Deaths

7.1.1. Adverse Event Dictionary

Clinical and laboratory adverse events (AEs) will be coded using the current version of MedDRA. System organ class (SOC), high level group term (HLGT), high level term (HLT), preferred term (PT), and lower level term (LLT) will be provided in the AE dataset.

7.1.2. Adverse Event Severity

Adverse events are graded by the investigator as Grade 1, 2, 3, or 4 according to toxicity criteria specified in the protocol. The severity grade of events for which the investigator did not record severity will be categorized as “missing” for tabular summaries and data listings, and the most severe will be considered (for sorting purpose only) in data presentation.

7.1.3. Relationship of Adverse Events to Study Drug

Related AEs are those for which the investigator selected “Related” on the AE CRF to the question of “Related to Study Treatment.” Events for which the investigator did not record relationship to study drug will be considered to be related to study drug for summary purposes. However, by-subject data listings will show the relationship as missing from that captured on the eCRF.

7.1.4. Serious Adverse Events

Serious adverse events (SAEs) will be identified and captured as SAEs if the AEs met the definition of SAE specified in the study protocol. Serious adverse events captured and stored in the clinical database will be reconciled with the SAE database from the Pharmacovigilance and Epidemiology Department before database finalization.

7.1.5. Treatment-Emergent Adverse Events

7.1.5.1. Definition of Treatment-Emergent

Treatment-emergent adverse events (TEAEs) are defined as 1 or both of the following:

- Any AEs with an onset date on or after the study drug start date and no later than 30 days after permanent discontinuation of study drug
- Any AEs leading to premature discontinuation of study drug

7.1.5.2. Incomplete Dates

If the onset date of the AE is incomplete, then the month and year (or year alone if month is not recorded) of onset determine whether an AE is treatment emergent, as long as the AE stop date is

not prior to the first dose date of study drug. The event is considered treatment emergent if both of the following 2 criteria are met:

- The AE onset and end date is the same as or after the month and year (or year) of the first dosing date of study drug, and
- The AE onset date is the same as or before the month and year (or year) of the date corresponding to 30 days after the date of the last dose of study drug

An AE with completely missing onset and stop dates, or with the onset date missing and a stop date later than the first dose date of study drug will be considered to be treatment-emergent.

7.1.6. Summaries of Adverse Events and Deaths

A brief high-level summary of TEAEs will be provided for the SOF/VEL 4 Week group. The number and percentage of subjects who had the following: any AE; any treatment-related AE; any AE of Grade 3 or above; any treatment-related AE of Grade 3 or above; any AE of Grade 2 or above; any treatment-related AE of Grade 2 or above; any SAE; any treatment-related SAE; any AE leading to premature discontinuation of SOF/VEL; and any AE leading to interruption of SOF/VEL. All deaths (including those that are treatment-emergent and those that are not treatment-emergent) observed during the study will also be summarized and included in this table.

Adverse event summaries will provide the number and percentage of subjects with TEAEs by SOC and PT for the SOF/VEL 4 Week group based on the the Safety Analysis Set as follows:

- All AEs
- All treatment-related AEs
- AEs of Grade 3 or above
- Treatment-related AEs of Grade 3 or above
- AEs of Grade 2 or above
- Treatment-related AEs of Grade 2 or above
- All SAEs
- Treatment-Emergent Non-Serious Adverse Events Occurring in At Least 5% of Subjects

Multiple events will be counted once only per subject in each summary. Adverse events will be summarized and listed first in alphabetic order of SOC and then by PT in order of descending incidence within an SOC. In summaries by severity grade, the most severe grade will be used for those AEs that occurred more than once in an individual subject during the study.

In addition to the above summary tables, TEAEs will also be summarized for the SOF/VEL 4 Week treatment group by PT only, in order of descending incidence for:

- AEs that occurred in > 1 subject
- AEs leading to interruption of SOF/VEL
- AEs leading to premature discontinuation of SOF/VEL
- All SAEs
- All treatment-related SAEs

In addition to the by-treatment summaries described above, by-subject data listings, with a variable indicating whether the event is treatment-emergent, will be provided for the following:

- All AEs
- AEs leading to premature discontinuation of SOF/VEL
- All AEs of Grade 3 or above
- SAEs
- All Deaths
- Graft Loss

7.1.7. Additional Analysis of Adverse Events

None

7.2. Laboratory Evaluations

Summaries of laboratory data will be provided for the Safety Analysis Set and will include data collected up to the last dose of study drug plus 30 days for subjects who have permanently discontinued the study drug. The analysis will be based on values reported in conventional units. When values are below the lower limit of quantitation, they will be listed as such, and the closest imputed value will be used for the purpose of calculating summary statistics as described in Section 3.7 of this SAP.

A by-subject listing for laboratory test results will be provided by subject ID number and visit in chronological order for screening lab tests, hematology, serum chemistry, and urinalysis separately. Values falling outside of the relevant reference range and/or having a severity grade of 1 or higher on the Gilead Grading Scale for Severity of Adverse Events and Laboratory Abnormalities will be flagged in the data listings, as appropriate.

A listing of the LabPlus laboratory normal ranges will be provided. Ranges are based on the sex and age of the patient on the date of collection of the laboratory sample.

No inferential statistics will be generated.

7.2.1. Summaries of Numeric Laboratory Results

Descriptive statistics (n, mean, SD, median, Q1, Q3, minimum and maximum) will be provided for the SOF/VEL 4 Week group by analysis visit for: ALT, aspartate aminotransferase (AST), alkaline phosphatase, total bilirubin, direct bilirubin, white blood cell (WBC), neutrophils (absolute), lymphocytes (absolute), reticulocyte count, hemoglobin, platelets, albumin, international normalized ratio of prothrombin time (INR), serum creatinine, and creatinine clearance (CrCl).

A baseline laboratory value will be defined as the last measurement obtained on or prior to the date/time of first dose of study drug. The mean, median, Q1, Q3, minimum and maximum will be displayed to reported number of digits, and SD to reported number of digits +1 for each on-treatment visit. The posttreatment Week 1, 2, and 4 visits will be presented as additional separate visits. In the case of multiple values in an analysis window, data will be selected for analysis as described in Section 3.8.3 of this SAP.

The number and percentage of subjects with at least 1 postbaseline (up to 30 days post last dose) hemoglobin value < 10 g/dL and < 8.5 g/dL will be summarized. The denominator will be the number of subjects with at least 1 postbaseline hemoglobin value.

A listing of subjects meeting the criteria for postbaseline hemoglobin < 10 g/dL and < 8.5 g/dL will be provided.

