If the transplant is completed before noon, the subject will take their first dose that day after the transplant which will be considered Day 1. If the transplant is completed after noon, the subject will take their first dose the following morning which will be considered Day 1. The planned first dose may be delayed for up to 1 day if, in the investigators opinion, delay is in the subject's medical interest. The subject will receive 4 weeks of study drug.

On-treatment assessments starting at Day 1 will include vital signs, ECG (only at Day 28), AEs, CMs (including immunosuppressive therapy), safety laboratory tests, estimated  $Cl_{cr}$ , HCV RNA, study drug dosing adherence and urine pregnancy tests (females of childbearing potential only).

Post-treatment assessments through Post-treatment week 4 only include AEs and CMs. Weight, vital signs, and urine pregnancy tests (females of child bearing potential only) will only be done at Post-treatment week 4. Pregnancy prevention counseling will be done at Post-treatment week 1 only. Safety laboratory tests, HCV RNA and viral sequencing samples will be collected through all Post-treatment visits.

Samples for viral RNA sequencing/phenotyping will be collected starting at Day 1 and every visit thereafter.

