## **8.6. Safety Analysis**

Safety will be evaluated by assessment of clinical laboratory tests, physical examinations, and vital signs measurements at various time points during the study, and by the documentation of AEs.

All safety data collected while “on treatment” (ie, on or after Study Day 1 up to 30 days after the last dose of study drug) will be summarized for subjects who receive SOF/VEL.

Safety endpoints will be summarized as the number (percentage) of subjects with events or abnormalities for categorical data or as an 8-number summary (n, mean, standard deviation, median, Q1, Q3, minimum, maximum) for continuous data.

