7.2.2. Graded Laboratory Values

The Gilead Grading Scale for Severity of Adverse Events and Laboratory Abnormalities will be used for assigning toxicity grades (0 to 4) to laboratory results. Grade 0 includes all values that do not meet the criteria for an abnormality of at least Grade 1. Some laboratory tests have criteria for both increased and decreased levels.

Toxicity grading will be presented in listings of laboratory data. No summary tables for toxicity grading will be produced due to the effects of liver transplantation on laboratory values in the immediate post-operative period.

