29.7*	Neutrophils ($\times 10^3/\mu\text{L}$) by Visit	Safety Analysis Set
29.8*	Lymphocytes ($\times 10^3/\mu\text{L}$) by Visit	Safety Analysis Set
29.9*	Reticulocyte Count ($\times 10^3/\mu\text{L}$) by Visit	Safety Analysis Set
29.10*	Hemoglobin (g/dL) by Visit	Safety Analysis Set
29.11*	Platelets ($\times 10^3/\mu\text{L}$) by Visit	Safety Analysis Set
29.12*	Albumin (g/dL) by Visit	Safety Analysis Set
29.13*	INR by Visit	Safety Analysis Set
29.14*	Serum Creatinine (mg/dL) by Visit	Safety Analysis Set
29.15*	Creatinine Clearance (mL/min)	Safety Analysis Set
30	Postbaseline Hemoglobin < 10 g/dL and < 8.5 g/dL	Safety Analysis Set
31.1	Pulse (bpm) by Visit	Safety Analysis Set
31.2	Diastolic Blood Pressure (mmHg) by Visit	Safety Analysis Set
31.3	Systolic Blood Pressure (mmHg) by Visit	Safety Analysis Set

* Included in DMC analysis.

PK Table or Figure Number	Title	Analysis Set
PK Table 1	Subjects Evaluable by Study Day 1 SOF/VEL Route of Administration	PK Substudy Analysis Set
PK Table 2	Plasma SOF Concentrations (ng/mL) by Subject with Summary Statistics for Each Substudy Timepoint (by Route of SOF/VEL Administration on Day 1)	PK Substudy Analysis Set
PK Table 3	Plasma GS-331007 Concentrations (ng/mL) by Subject with Summary Statistics for Each Substudy Timepoint (by Route of SOF/VEL Administration on Day 1)	PK Substudy Analysis Set
PK Table 4	Plasma GS-566500 Concentrations (ng/mL) by Subject with Summary Statistics for Each Substudy Timepoint (by Route of SOF/VEL Administration on Day 1)	PK Substudy Analysis Set
PK Table 5	Plasma VEL Concentrations (ng/mL) by Subject with Summary Statistics for Each Substudy Timepoint (by Route of SOF/VEL Administration on Day 1)	PK Substudy Analysis Set
PK Table 6	Plasma SOF Pharmacokinetic Parameters by Subject with Summary Statistics for Each Parameter (by Route of SOF/VEL Administration on Day 1)	PK Substudy Analysis Set
PK Table 7	Plasma GS-331007 Pharmacokinetic Parameters by Subject with Summary Statistics for Each Parameter (by Route of SOF/VEL Administration on Day 1)	PK Substudy Analysis Set
PK Table 8	Plasma GS-566500 Pharmacokinetic Parameters by Subject with Summary Statistics for Each Parameter (by Route of SOF/VEL Administration on Day 1)	PK Substudy Analysis Set
PK Table 9	Plasma VEL Pharmacokinetic Parameters by Subject with Summary Statistics for Each Parameter (by Route of SOF/VEL Administration on Day 1)	PK Substudy Analysis Set

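### Table 30 counts any low post-baseline hemoglobin without regard to baseline, so subjects already low after surgery are pooled with those who become newly low

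*SAP*

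**What the plan says.** SAP Section 7.2.1 sets the numerator of Table 30 as subjects with at least one post-baseline "hemoglobin value < 10 g/dL and < 8.5 g/dL will be summarized", looking up to 30 days past the last dose. On the denominator it says: "The denominator will be the number of subjects with at least 1 postbaseline hemoglobin value". Neither sentence refers to the baseline value. The output list in SAP Section 12 titles the table "Postbaseline Hemoglobin < 10 g/dL and < 8.5 g/dL", and Listing 20 names the subjects who meet the criteria. No shift from baseline or baseline category is specified for either output.

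The same section defines baseline: "A baseline laboratory value will be defined as the last measurement obtained on or prior to the date/time of first dose of study drug". According to the protocol synopsis, when the transplant ends before noon "the subject will take their first dose that day after the transplant which will be considered Day 1". Otherwise the first dose is given the next morning, and a delay of up to one day is allowed. A pre-dose Day 1 sample is therefore post-operative. If there is none, protocol Section 8.3 says that "a missing Day 1 result will be replaced with the most recent non-missing screening result, if available". The scheduled screening and pre-surgery samples precede the transplant.

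Two further places bear on how the table will be read. SAP Section 7.2.2 states: "No summary tables for toxicity grading will be produced due to the effects of liver transplantation on laboratory values in the immediate post-operative period". Protocol Section 8.6 describes its on-treatment safety window as "on or after Study Day 1 up to 30 days after the last dose of study drug", which has the same upper limit as Table 30.

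**The concern.** Table 30 is the only planned table that counts subjects by a laboratory threshold. Two different histories produce the same entry: low after surgery and slow to recover, or adequate before dosing and low afterwards. Only the second says anything about what happened after SOF/VEL was started.

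The documents make it plausible that some subjects start low. Protocol Section 1.1 says that liver transplant patients often have reduced blood cell counts at baseline. The summary of the decompensated-cirrhosis study in protocol Section 1.7 lists decreased hemoglobin among the most common Grade 3 or 4 hematology findings, and ascribes these findings to ribavirin or to the liver disease. Neither statement gives a post-operative hemoglobin value.

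Safety and tolerability is a primary objective, there is no control arm, and about 10 subjects are planned, so each subject moves the percentage by about 10 points. A high figure could be taken as frequent anemia arising after the start of treatment when nobody had worsened.

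**Working it through.** **The plan's own figure.** The Table 30 rule states no number. The only design figure is the maximum length of 63% for an exact 95% interval with 10 subjects. It reproduces: the widest Clopper-Pearson interval is at 5/10, from 18.71% to 81.29%, a length of 62.58%. It matters here only because it fixes n = 10.

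**The counting rule.** For one threshold, let N be the subjects with a post-baseline value, L those below the threshold before dosing, b those of the L who are below it at least once later, and w those not below it before dosing who are below it later. Then:

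- Table 30 as written = (b + w)/N
- count among subjects at or above the threshold at baseline = w/(N − L)

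Take N = 10, nobody newly low (w = 0), and every subject low at Day 1 still low at the next draw (L = b). The values of b are assumptions.

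| b | Table 30 | Baseline-conditioned |
|---|---|---|
| 2 | 2/10 = 20% | 0/8 |
| 5 | 5/10 = 50% | 0/5 |
| 8 | 8/10 = 80% | 0/2 |

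The opposite case, L = b = 0 and w = 5, also gives 5/10 in Table 30 but 5/10 in the conditioned count. Table 30 alone cannot tell this from the middle row.

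**When baseline is pre-transplant.** Suppose 2 of the 5 low subjects in the middle row have no post-transplant pre-dose sample and were above the threshold before surgery. A plain split by baseline would class them as adequate at baseline and newly low: 2/(10 − 3) = 2/7, although nobody fell after dosing. With those two in their own row, the main row is 0/(8 − 3) = 0/5 and the separate row is 2/2.

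**Illustration with no drug effect.** Assumed inputs: Day 1 mean 9 to 11 g/dL, between-subject SD 1.2, visit-to-visit SD 0.5, recovery 0 to 0.5 g/dL per week, and nine post-baseline draws (Days 3, 5, 7, 14, 21 and 28, and post-treatment Weeks 1, 2 and 4).

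| | < 10 g/dL | < 8.5 g/dL |
|---|---|---|
| Counted in Table 30 | 25% to 92% | 3% to 58% |
| Newly low, of all subjects | 8% to 23% | 1.5% to 24% |
| Newly low, of those not low at baseline | 10% to 66% | 1.5% to 36% |

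In the middle scenario (mean 10, recovery 0.3), Table 30 shows 59.1% below 10 g/dL. Of this, 13.0 points are newly low and 59.1 − 13.0 = 46.1 points were already low. The last row of the table shows the limit of the remedy: with no drug effect at all, visit-to-visit variation alone makes some subjects newly low.

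**The case against.** A reader might infer that the SAP reports surgical anemia as an on-treatment or drug-related abnormality. The documents do not support that. The text and title of Table 30 say post-baseline, and the count delivers exactly that. SAP Section 3.8.2 limits on-treatment laboratory data to the last dose plus 3 days, well short of the 30 days used here. Only the broad safety window in protocol Section 8.6 carries an on-treatment label, and nothing attributes the count to SOF/VEL.

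Nor is information lost. Listing 16.1 gives each subject's hemoglobin in chronological order, with abnormal or graded values flagged. Listing 20 identifies those who meet the criteria. Table 29.10 gives by-visit summaries, including minimum and maximum. With about 10 subjects, every crossing can be traced by hand.

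The consequences are limited too. Table 30 is descriptive and is not marked for the data monitoring committee, whereas Table 29.10 and Listing 16.1 are. The primary safety endpoint is adverse events leading to discontinuation. Anemia needing intervention is recorded as an adverse event, although protocol Section 7.5 exempts most direct transplant sequelae. Section 7.2.2 concerns tables of toxicity grades, so keeping one fixed-threshold count is a tension with its reasoning rather than a contradiction.

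Finally, a baseline split cannot remove a surgical fall that occurs after the first dose. It also misclassifies subjects whose baseline is pre-transplant. Appendix 2 of the protocol schedules Day 1 hematology without saying that it must be drawn before the dose.

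All of this stands, and it bounds the point. It does not supply what is missing: no planned table separates subjects who were low before dosing from those who became low afterwards.

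**Conclusion.** The point holds as a minor one about interpreting a descriptive table. The rule in Section 7.2.1 ignores baseline, in a setting where Section 7.2.2 itself treats post-operative effects as a reason for not tabulating grades. If b of 10 subjects are low at Day 1 before dosing and still low at the next draw, Table 30 shows at least b/10 with no newly low subject. That statement is exact; the value of b is unknown. It would be tempting to say that the table will be dominated by pre-dose status, but the documents give no hemoglobin distribution, and every percentage in the working rests on assumed values. No efficacy result, sample size or committee output changes.

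**What to change.** - Keep the all-subject row of Table 30.
- For each threshold, add the count among subjects at or above it at baseline, using baseline categories ≥ 10, 8.5 to < 10, and < 8.5 g/dL.
- For this split only, define baseline as the last value after the transplant and before the first dose. Show subjects who have only a pre-transplant baseline in a separate row, so that the surgical fall is not counted as new.
- In Listing 20, show baseline hemoglobin and its sample date and time relative to the transplant.
- Add a footnote that the split removes pre-dose status only and does not separate later surgical falls from a drug effect.

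The cost is one extra breakdown in one table and a few listing columns. The SAP already uses laboratory sample date and time for its baseline window and lists transplant end and first-dose times, so no new data are needed. The downside is small denominators, 2 to 8 in the assumed examples, so counts should be shown alongside any percentage.
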